### **Visit 3 (Visit 3 will occur 1-2 weeks (+/- 3 days) after Visit 2.)**

- Study participants will be asked to repeat the study protocol described under Visit 2, and at that time, they will be crossed over to either active drug treatment or placebo, depending on their assigned treatment sequence.

Study staff will contact the participant approximately 2 weeks after visit 3 to assess for adverse events.

Table 1 presents the schedule of procedures for this study.

Table 1.

	Visit 1	Visit 2 and Visit 3						
		Prior to Dose 1	Dose 1	Immediately After Dose 1	Dose 2	Immediately After Dose 2	10 minutes after Maximal Exercise Test	Dose 3
Elapsed Time								
Procedures:								
Informed consent	X							
Demographics and medical history	X	X d						
Concomitant Medication Review	X	X						
Vital signs	X	X		X f		X f		X f
Resting ECG		X						
Urine pregnancy	X	X						
Randomization	X							
Administer Drug			X		X			X
Venous Pressure a						X		X
Spirometry	X c					X c		
Vascular Function (FMD/PWV)				X			X e	
Shear Wave Elastography				X			X (immediate post max exerc test)	
Maximal Exercise Ramp Test	X e					X		
Venous Structure and Function	X							
Exercise Endurance Test	X							X
Complete Metabolic Panel b , Once only, at visit 2 or 3		X						
CBC, GGT Once only at visit 2 or 3		X						
Adverse Event Monitoring	X	X	X	X	X	X	X	X

a. Venous pressure will be measured from before exercise test, every 1 minute during exercise, until 5 minutes after exercise. Cannula for venous pressure may be placed early in the day to facilitate scheduling.

b. Complete metabolic panel will include: sodium, potassium, chloride, carbon dioxide, BUN, creatinine, calcium, glucose, albumin, total protein, AST, ALT, ALP, and total bilirubin.

c Spirometry will occur prior to maximal exercise test.

[figure not shown]
d Prior to exercise testing, if medical history or adverse event questioning reveals intercurrent chest infection, wheezing, or other respiratory condition, study staff will consult with PI or designee to determine if exercise testing should proceed.

e Patients will be given a light meal during visit 1 and after the 2nd vascular test is completed at visits 2 and 3.

f Blood pressure will be monitored for 30 minutes post study drug administration (immediately, 15 min, and 30 min).. Window for blood pressure measurements is +/- 3 minutes. If no drop in BP below threshold levels following previous study drug administration, then BP will not be monitored for subsequent doses. Threshold levels for additional monitoring are a drop in systolic pressure below 90 mm Hg (or 85 mg Hg if baseline was  $\leq$  90 mm Hg) or drop of  $\geq$  30 mm Hg from baseline.

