## **6. STUDY PROCEDURES**

All study procedures will occur at Cincinnati Children's Hospital Medical Center (CCHMC) main campus. The Heart Institute (HI) at CCHMC has an adult heart clinic where patients may be seen as well. The HI adult clinic is on site at the main hospital campus and therefore has full access to emergency medical staff onsite at the hospital. Participants will be asked to fast for 8-12 hours prior to each study visit. Participants taking vasodilators (ACE inhibitors, angiotensin receptor blockers) will be asked to not take their medication on the day of the study for each visit, but can continue to take vasodilators in between visits. Participants will receive a light meal at the visits after completing the part of assessments that require fasting.

The following procedures will occur during the study:

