### Visit 2 (Visit 2 will occur 1-2 weeks (+/- 3 days) after Visit 1)

- Insertion of venous cannula will be placed early in the visit to be used for taking venous pressure during the exercise testing.
- Vital signs (heart rate, blood pressure, oxygen saturation, height and weight)
- Blood drawn for metabolic panel (CMP), GGT, CBC (Drawn once at visit 2 or visit 3)
- Review of Concomitant Medications
- Urine pregnancy testing
- Resting ECG
- First dose of treprostinil OR placebo, as determined by the randomization following Visit 1.
- Participant blood pressure will be monitored for  $\frac{1}{2}$  hour (immediately, 15 min, and 30 min.) following the initial dose of treprostinil or placebo on a particular study day.
  - If systolic BP drops below 90 mm Hg or drops  $\geq 30$  mm Hg from the baseline, the participant's blood pressure will be monitored until return to above these thresholds. If baseline systolic blood pressure is below 90 mm Hg, then

the low threshold for additional monitoring will be 85 mm Hg for these participants.

- Study staff monitoring the blood pressure will consult with the PI or MD subI should a drop in blood pressure meeting these thresholds occur. Patient will continue with the investigation at the discretion of the PI or MD subI.
- Shear Wave Elastography (for liver stiffness)
- Vascular function assessment (Pulse Wave Velocity [PWV] and brachial Flow Mediated Dilation [FMD], already in use in this institution (described below).
- If the participant tolerated the 1st dose of treprostinil or placebo, (i.e no clinically significant drop in blood pressure or unexpected AEs deemed by the PI or MD subI to be related to study drug that would preclude the patient from continued participation) they will receive a 2nd dose of their assigned treatment (at least 2 hours after the first dose).
- If the patient did not experience a significant drop in blood pressure (as defined previously) following the 1st dose, then no further blood pressure monitoring will be required prior to the exercise test.
- If the participant experienced a drop in blood pressure (as defined previously) following the 1st dose, then blood pressure will be monitored for ½ hour (immediately, 15 min, and 30 min.) following the 2nd dose of treprostinil or placebo.

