  - If systolic BP drops below 90 mm Hg or drops  $\geq$  30 mm Hg from the baseline for visit 2/visit 3, the participant's blood pressure will be monitored until return to above these thresholds.
  - Study staff monitoring the blood pressure will consult with the PI or MD subI should a drop in blood pressure meeting these thresholds occur. Patient will continue with the investigation at the discretion of the PI or MD subI.
- Venous pressure manometer set-up (including calibration) will then be conducted prior to commencing exercise testing during which the venous pressures will be measured continuously during the exercise test.
- Maximal exercise testing/Ramp protocol (including spirometry).
- Immediately following exercise, a shear wave liver elastography will be repeated
- Post recovery, vascular function assessment (FMD and PWV) will be repeated.
- Light meal followed by a break for complete exercise recovery
- If the participant tolerated the prior dose of treprostinil or placebo, (i.e no clinically significant AEs deemed by the PI or MD subI to be related to study drug that would preclude the patient from continued participation) they will receive a 3rd dose of their assigned treatment.

- If the patient did not experience a significant drop in blood pressure (as defined previously) following the prior dose, then no further blood pressure monitoring will be required prior to the exercise test.
- If the participant experienced a drop in blood pressure following the previous dose, then blood pressure will be monitored for  $\frac{1}{2}$  hour (immediately, 15 min, and 30 min.) following the 3rd dose of treprostinil or placebo.
  - If systolic BP drops below the thresholds described previously, the participant's blood pressure will be monitored until return to above these thresholds.
  - Study staff monitoring the blood pressure will consult with the PI or MD subI should a drop in blood pressure meeting these thresholds occur. Patient will continue with the investigation at the discretion of the PI or MD subI.
- Endurance exercise test at 80% peak exertion to occur 2 hours after the maximal exercise testing. This is expected to last about 4-7minutes.
  - Venous pressures will be measured during the exercise test as described herein (see Venous Cannulation).
- The participants will be observed for 60 minutes following medication administration.
- Adverse event monitoring

The visit is anticipated to take 5-6 hours.

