## Maximal Exercise Testing/Ramp Protocol

The {ParvoMedics Exercise cart with Blue Cherry software} will be used for cardiopulmonary exercise testing in all cases. The equipment will be calibrated and operated to the standards specified in the ATS/ACCP (2003) guidelines. Participants will initially sit at rest on the electromagnetically-braked cycle ergometer for three minutes while baseline cardiopulmonary variables are recorded (baseline phase). This will be followed by three minutes of unloaded cycling at a cadence of 60 rpm, after which the power output will be increased by 15 Watts per minute until the limit of tolerance. Talking to the study subjects will be kept to a minimum. Participants will be asked to maintain a cadence of 60 rpm throughout the test until volitional intolerance. The power output will be immediately reduced to zero and the cardiopulmonary variables monitored for at least 5 minutes (recovery phase). Transcutaneous CO2 monitoring will be done throughout the exercise test. Venous pressures will be monitored during exercise as described above (see Venous Cannulation).

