## **Endurance Exercise Testing**

Exercise endurance is a highly sensitive measure of functional outcome following interventions (Oga et al., 2000; Borel et al., 2013). Two hours after ramp incremental exercise testing (CPET) a constant work rate exercise test will be performed to determine exercise endurance; 2 hours is sufficient for complete recovery of exercise endurance following prior exhaustive exercise (Ferguson et al., 2010). The primary outcome from this assessment is exercise duration; standard CPET variables will also be measured throughout to provide physiological interpretation for exercise endurance change. A power output corresponding to 80% of the peak power achieved during the ramp incremental test will be calculated. After ~ 3 minutes at unloaded cycling, the power will be increased abruptly to 80% peak power: The subject will be encouraged to continue for as long as possible and the duration recorded. The target duration for this exercise test at baseline is 4-7 minutes and is typically achieved at 80% peak power (van der Vaart et al., 2013). In the event that the exercise endurance test duration falls outside of this 'optimal' range at the first visit, the power output may be adjusted by 5 Watts (or 10% rounded to the nearest 5W, whichever is greater) and this adjusted power used for all subsequent tests.

Exercise endurance change, and well as change in "isotime" physiologic variables (comparison between physiologic values during active drug and placebo measured at the same time points during exercise), including central venous pressure and vo2, between tests with placebo and inhaled treprostinil will be calculated.

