## **9. DATA ANALYSIS**

### **9.1. Study Endpoints**

The primary endpoint is exercise endurance time (seconds).

The secondary endpoints are the following:

- Peak VO2
- Ventilator equivalent for CO2 at the lactate threshold
- Oxygen uptake efficiency slope
- Lactate threshold
- Pulmonary blood flow
- Pulse wave velocity
- Augmentation Index
- Shear wave elastography (measure in velocity [m/s]), the mean of 10 measurements will be taken.
- Safety endpoints will include: a drop in systolic systemic blood pressure of greater than 30 mm Hg if SBP >120mm Hg, or a drop in BP to <90 mm Hg if resting BP is less than 120mmHg.

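### After a clean Dose 1, no blood pressure reading is required after Doses 2 and 3, so the Dose 3 rule waits on an unmeasured event and the 9.1 endpoint is systematically ascertained only after Dose 1

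*Combined protocol and SAP*

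**What the plan says.** Section 6 gives three doses of treprostinil or placebo at Visit 2 and again at Visit 3. Under Medication Administration, Dose 1 is the test dose, Dose 2 precedes the maximal test and Dose 3 precedes the endurance test. BP is taken in everyone immediately, 15 minutes and 30 minutes after Dose 1.

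The rules for the later doses are conditional:

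- **Dose 2** (Visit 2 list): without a significant drop after Dose 1, "then no further blood pressure monitoring will be required prior to the exercise test".
- **Dose 3** (same list): the same waiver applies if there was no drop after the prior dose. Otherwise, "If the participant experienced a drop in blood pressure following the previous dose, then blood pressure will be monitored for" half an hour.
- **Table 1, footnote f**: "If no drop in BP below threshold levels following previous study drug administration, then BP will not be monitored for subsequent doses". The vital-signs entries after Doses 2 and 3 carry this footnote, so they are conditional too.
- **Blood Pressure Monitoring**: staff may take extra readings at their discretion, and a threshold drop calls for monitoring at the next dose.

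Section 9.1 states: "Safety endpoints will include: a drop in systolic systemic blood pressure of greater than 30 mm Hg if SBP >120mm Hg". It adds a fall below 90 mm Hg when resting pressure is under 120. It names no dose or time window, and 9.2 describes no safety analysis.

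**The concern.** There are two consequences for a participant with no Dose 1 drop.

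The first concerns conduct. The protocol wants BP watched after Dose 3 in anyone who dropped after Dose 2. In this participant nothing scheduled would show a Dose 2 drop, so an unmeasured result is handled as no drop. The condition for giving Dose 3 does not close the gap. The condition for Dose 2 mentions BP, but the one for Dose 3 mentions only clinically significant adverse events.

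The second concerns reporting. If the 9.1 endpoint is reported as a rate over the whole dosing day, doses with no reading would count as doses without a drop. Doses 2 and 3 are the ones given before exercise, and their circumstances differ from those of Dose 1. For Dose 1, "Participants will be asked to fast for 8-12 hours prior to each study visit", and the vascular tests that follow are done supine at rest. Dose 3 comes after a maximal exercise test and then "Light meal followed by a break for complete exercise recovery".

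**Working it through.** The plan gives no figure for BP drops, so there is none of its own to reproduce. The only input is N=26 from 9.3. That number is sound enough to use: a paired t test with a 37 s change and SD 65 s has 79.7% power at 26. Nothing below depends on this power.

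**1. Doses with a reading scheduled in everyone (all 26 complete)**

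| | Whole trial | Per treatment |
|---|---|---|
| All doses | 26 × 2 × 3 = 156 | 26 × 3 = 78 |
| Dose 1: readings in everyone | 26 × 2 = 52 | 26 |
| Doses 2 and 3: conditional | 156 − 52 = 104 | 78 − 26 = 52 |

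Systematic ascertainment therefore covers 26/78, one third of doses per treatment.

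**2. How far scheduled readings alone reach into the conditional 52**

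Suppose k participants drop after Dose 1 on a given treatment. At most k are then monitored after Dose 2, and at most k after Dose 3 (if they drop again), giving at most 2k of 52:

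- k = 0: 0 of 52
- k = 2: 4 of 52 (7.7%)
- k = 5: 10 of 52 (19.2%)

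The values of k are illustrations. 2k is not a ceiling on all readings, because a drop found by a discretionary reading after Dose 2 also triggers monitoring after Dose 3.

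**3. The Dose 3 rule by pattern**

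| After Dose 1 | After Dose 2 | Dose 3 rule | Visible from scheduled readings? |
|---|---|---|---|
| drop | drop | monitor | yes |
| drop | none | do not monitor | yes |
| none | drop | monitor | no |
| none | none | do not monitor | no |

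The last two rows cannot be told apart from scheduled data. The rule works for participants who dropped after Dose 1 and lacks its input for the rest.

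**4. What a clean Dose 1 result would support**

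If 0 of 26 drop after Dose 1, the exact two-sided 95% upper limit is 1 − 0.025^(1/26) = 13.2%. It applies to Dose 1 only.

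**5. Which threshold defines a drop**

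The Blood Pressure Monitoring thresholds and the 9.1 definition do not coincide:

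- Baseline 88 falling to 86 is below 90, so it meets 9.1. It is not below 85 and the fall of 2 is less than 30, so it does not meet the monitoring threshold.
- Baseline 130 falling to 100 is a fall of exactly 30. It meets the monitoring threshold (30 or more) but not 9.1 (more than 30).
- A baseline of exactly 120 falls under neither branch of 9.1.

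**The case against.** The strongest reply is that the schedule is a choice. Dose 1 is a named test dose, all three doses are 18 mcg, and footnote f clears subsequent doses in the plural. On that reading the Dose 3 rule is meant for participants who dropped after Dose 1, and for them it works. This largely stands. A reader might infer that the rules contradict each other or that the Dose 3 rule has no effect after a clean Dose 1, but the text supports neither. A Dose 2 drop found by symptoms or a discretionary reading would properly trigger monitoring after Dose 3. What remains is that no required reading looks for such a drop.

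A reader might also infer that there will be no BP data at all around exercise. That is not established. In the ramp test, "Participants will initially sit at rest on the electromagnetically-braked cycle ergometer for three minutes while baseline cardiopulmonary variables are recorded", and in the endurance test "standard CPET variables will also be measured throughout to provide physiological interpretation for exercise endurance change". Neither section lists the variables, so BP may or may not be among them. The waivers cover only the period before each test.

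Other safeguards count as well: 60 minutes of observation, adverse event monitoring, and DSMB review after the first two patients and then every eight. They lower the risk from symptomatic drops but do not give systematic data on asymptomatic ones.

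Finally, nothing in the documents shows that BP falls more after Dose 3 than after Dose 1, and a recovery break is specified. The different circumstances are a reason to measure, and no evidence of greater harm. The Blood Pressure Monitoring section also has figures that were not available for this review. Footnote f and the Visit 2 rules are explicit without them.

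**Conclusion.** The point holds as a modest, inexpensive improvement. For participants clear after Dose 1, the trigger for Dose 3 monitoring is an event that no required reading would detect. The 9.1 endpoint is systematically ascertained after 26 of 78 doses per treatment. Readings after the other 52 depend on an earlier drop found by a scheduled or discretionary measurement.

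The counts assume that all 26 participants complete both visits and receive all three doses at each. They also assume that BP is not already a routine exercise-test variable; if it is, the gap is smaller. The documents give no drop rate, so the number of missed drops cannot be estimated, and a claim that the trial will miss a material share would go beyond them. The finding does not affect the primary analysis or N=26.

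**What to change.** **Section 6 and footnote f.** Require one cuff reading in everyone at a fixed, stated time after Dose 2 and after Dose 3, the same at both visits. Table 1, footnote a already has venous pressure measured before each exercise test, which gives a slot both times. Use the arm without the cannula. Apply the Blood Pressure Monitoring thresholds before exercise starts. If a resting BP is already recorded for the exercise tests, say so and use it.

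**Section 9.2.** Report drops by dose, with the number measured after each. State whether the Blood Pressure Monitoring thresholds or the 9.1 definition defines a drop. Base the treprostinil–placebo comparison on Dose 1 and do not present it as a three-dose rate. If no readings are added, this reporting change is the minimum and needs no extra procedure.

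**Cost.** Up to 2 doses × 2 visits × 26 = 104 extra cuff readings, plus short text edits. One reading is less sensitive than the three taken after Dose 1, so rates are not directly comparable across doses. A low reading may delay the endurance test, possibly more often on active drug, which would alter the interval between dose and primary endpoint. Record the dose-to-test time so that this can be seen.

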## Blood Pressure Monitoring

Blood Pressure will be monitored following administration of treprostinil or placebo dosing as shown below. Additional blood pressure monitoring may occur at any time during the procedure at the discretion of study staff for patient safety.

[figure not shown]

If Baseline Systolic BP is:	Threshold for additional monitoring is:	Action Taken
≥90 mg Hg	drop in systolic BP to < 90 mm Hg OR drop in systolic BP of ≥ 30 mm Hg from baseline	Monitor BP until return to baseline PI or MD subI assess if patient can continue Monitor BP at next dose: immediately, 15 min, 30 min
<90 mg Hg	drop in systolic BP to < 85 mm Hg OR drop in systolic BP of ≥ 30 mm Hg from baseline	Monitor BP until return to baseline PI or MD subI assess if patient can continue Monitor BP at next dose: immediately, 15 min, 30 min

[figure not shown]
## Medication Administration:

Inhaled treprostinil will be administered using the Tyvaso® inhalation system. A dose of 18mcg (3 breaths) or placebo (3 breaths) will be administered prior to the vascular function assessment (this will serve as a test dose to assess adverse effects), prior to the maximal exercise test (at minimum, 2 hours post initial dose) and then again prior to the endurance exercise test.

## Visit 1:

## Visits 2 and 3:

## Vascular Function Assessment

All patients will undergo vascular function assessment, at rest and in the supine position using noninvasive imaging and non-imaging techniques.. Ultrasound imaging techniques will include Venous Structure and Function and FMD. PWV is a non-imaging technique utilizing tonometry. Descriptions of the specific techniques are listed below. PWV and FMD will be repeated post exercise in supine position.

### Pulse wave velocity

The average of 3 PWV will be measured with a SphygmoCor CPV (AtCor Medical, Sydney, Australia).. This device measures pressure waveforms using a pencil-like probe, called a tonometer, placed on the neck and groin. The average of 3 distance measurements from carotid artery (neck) to sternal notch to femoral artery (groin) will be calculated for path length. ECG R-wave gated arterial waveforms are recorded from the carotid and femoral arteries. PWV is the difference in the carotid-to-femoral path length divided by the difference in R wave of the ECG to foot of the pressure waveforms. Higher PWV indicates stiffer conduit vessels.

### Brachial Flow Mediated Dilatation (FMD)

#### Forearm Reactivity Method (Brief)

After 10 minutes of rest in a temperature monitored room, fasting subjects will undergo assessment of brachial FMD according to published guidelines after refraining from ingesting caffeine, using tobacco or exercising for 8 hours.

Generally, the procedure will be performed on the right arm. All deviations from the protocol will be documented. The B-mode ultrasound imaging will be obtained with a Philips CX-50 (Amsterdam, Netherlands) portable ultrasound unit and the diameter of the right brachial artery is measured with a high resolution linear array L 12-3 MHz transducer with the subject in the supine position with the right arm extending 80-90 degrees from the body. A pneumatic BP tourniquet is applied to the widest part of the forearm below the antecubital fossa. Images are obtained at baseline pre-inflation 2-15 cm above the elbow. The imaging angle, imaging depth, overall gain, TGC, reject settings are used obtain an optimal image which shows a segment with clear anterior and posterior intimal interfaces between the lumen and vessel wall and two parallel lines representing echoes that arise from the blood intima and media adventitia boundaries on the near and far walls. Anatomic landmarks (veins, arterial branches, and/or fascial planes) are noted as an X on the imaging screen for reproducible transducer placement. The BP cuff is inflated to a minimum of 250 mmHg. After 5 minutes the tourniquet is deflated and reactive hyperemic 2D images and pulse wave Doppler waveforms are obtained at 60, 90, and 120 seconds post cuff deflation. End diastolic measures at the peak of the ECG R wave are acquired on the Digisoinics DigiView (Houston, Texas) DICOM storage and measuring software. 2D distance diameter measures are acquired 3 times from the blood /intima interfaces of near wall to far wall at each time point (baseline and 60 sec, 90 sec, and 120 sec post cuff deflation). Pulse wave Doppler is acquired at baseline, upon cuff deflation and post deflation (60, 90, 120 secs.) Peak systolic

velocity (PSV) is measured at each time point. Time velocity integral (TVI) and area under the curve are measured at baseline and on the 4th, 5th, and 6th beats post cuff deflation.

